12.3.2 Background Characteristics

Unless otherwise specified, this section applies to both Parts A and B. All summaries will be based on the Safety Set of the corresponding part overall. For Part A, and Part B if the weight-based 2 doses are used, the summary by the dosing groups (LUM 100 mg/IVA 125 mg q12h and LUM 150 mg/IVA 188 mg q12h) at enrollment determined by weight at the Screening Visit will be provided as supplementary information, unless otherwise specified. No statistical hypothesis testing will be performed.

12.3.2.1 Subject Disposition

Number and percentage of subjects in the following categories will be summarized as appropriate.

Numbers of the following categories will be provided:

- All Subjects Set
- Dosed (Safety Set)
- Enrolled and dosed (FAS, Part B only)

Both numbers and percentages of subjects in the following categories will be provided. The percentage will be based on the number in Safety Set of the corresponding part.

- Completed study drug treatment
- Prematurely discontinued the treatment and the reasons for discontinuations
- Completed study
- Prematurely discontinued the study and the reasons for discontinuations

For Part B, similar disposition tables will be provided based on the LCI Substudy Set.

12.3.2.2 Demographics and Baseline Characteristics

Demographic, background (e.g., medical history), and baseline characteristics will be summarized. Important protocol deviations/violations will be provided as a subject data listing only. The rules used to define the important protocol deviations/violations will be provided in the SAPs.

The demographics, baseline characteristics, and medical history summary will be presented for the Safety Set of the corresponding part to allow review of the characteristics of those included in safety analyses, which will be based on this analysis set.

For Part B, similar tables for demographics and baseline characteristics will be provided based on the LCI Substudy Set.

12.3.2.3 Prior and Concomitant Medications

Medications used in this study will be coded by using the World Health Organization Drug Dictionary Enhanced and categorized as the following:

- **Prior medication:** any medication that started before initial dosing of study drug in each part, regardless of when it ended.
- Concomitant medication: medication continued or newly received at or after initial dosing of study drug in each part to 14 days after the last dose of study drug in the corresponding part.
- **Post-treatment medication:** medication continued or newly received after 14 days after the last dose of study drug in each part.

A given medication can be classified as a prior medication, a concomitant medication, or a post-treatment medication; both prior and concomitant; both concomitant and post-treatment; or prior, concomitant, and post-treatment. If a medication has a missing or partially missing start/end date or time and it cannot be determined whether it was taken before initial dosing, concomitantly, or after 14 days after the last dose of study drug, it will be considered as prior, concomitant, and post-treatment.

Prior medications and concomitant medications will be summarized descriptively based on the Safety Set. Post-treatment medications will be listed for each subject.

12.3.2.4 Study Drug Exposure

Duration of study drug exposure is defined as follows: last dose date – first dose date + 1 day, regardless of any interruptions in dosing. If the last dose date of study drug is missing, the subject's last exposure date will be used for analysis purposes.

Part A

Study drug exposure will be summarized overall based on Part A Safety Set. In addition, the summary by the dosing group (LUM 100 mg/IVA 125 mg q12h and LUM 150 mg/IVA 188 mg q12h) at enrollment determined by weight at the Screening Visit will be provided as supplementary information.

Study drug exposure will be presented in an individual subject data listing to indicate whether the study drug was taken or not.

Part B

Duration of study drug exposure will be summarized overall based on Part B Safety Set and descriptively as a quantitative variable (number, mean, SD, SE, median, minimum, and maximum). If the weight-based 2 doses are used in Part B, summary by dosing groups (LUM 100 mg/IVA 125 mg q12h and LUM 150 mg/IVA 188 mg q12h) at enrollment determined by weight at the Screening Visit will be provided as supplementary information.

Additionally, the cumulative duration of treatment exposure, defined as the sum of the subject's duration of treatment exposure and expressed in subject-years, will be provided. Duration of exposure will also be summarized as a categorical variable.

12.3.2.5 Study Drug Compliance

Part A

Compliance will be presented in an individual subject data listing.

Part B

Study drug compliance will be assessed by calculating as follows: $100 \times (1 - [total number of days of study drug interruption] / [duration of study drug exposure + total number of days study drug interrupted after last dose, if any]). The total number of days of study drug interruption is defined as the sum of (number of days of each study drug interruption), where number of days of each study drug interruption is defined as the interruption end date – the corresponding interruption start date + 1.$

Percent of stick packs taken will be calculated as follows: $100 \times (\text{total number of stick packs administered}) / (2 \times [\text{duration of study drug exposure in days + total number of days study drug interrupted after last dose, if any]). Subjects who have a calculated percent of stick packs taken >100% will be considered as having taken 100% of stick packs.$

Treatment compliance percentages and percent of stick packs taken will be summarized descriptively as quantitative variables (number, mean, SD, SE, median, minimum, and maximum). The number and percentage of subjects whose compliance is <80% or $\ge80\%$ and the number and percentage of subjects whose percent of stick packs taken is <80% or $\ge80\%$ will be summarized.

Study drug compliance will be based on Part B Safety Set overall. If the weight-based 2 doses are used in Part B, supplementary information will be provided for study drug compliance by the dosing group (LUM 100 mg/IVA 125 mg q12h and LUM 150 mg/IVA 188 mg q12h) at enrollment determined by weight at the Screening Visit.

12.3.3 Pharmacodynamics Analysis (Part B Only)

12.3.3.1 Analysis of Primary Endpoints

Not applicable.

12.3.3.2 Analysis of Secondary Pharmacodynamic Endpoints

Analyses for secondary PD endpoints are described in Sections 12.3.3.2.1 through 12.3.3.2.13. Analyses for other secondary endpoints and sensitivity analysis, supportive analysis, subgroup analysis of secondary variables, and analyses for other endpoints will be described in the SAP.

12.3.3.2.1 Absolute Change From Baseline in Sweat Chloride at Week 24

For each subject and at each time point, 2 sweat chloride measurements will be collected: 1 from the right arm and 1 from the left arm. Of the 2 measurements, only the sweat chloride value obtained from a sample volume $\geq 15~\mu L$ will be included in any analysis (i.e., values from samples with volumes $<15~\mu L$ will be considered missing for analysis purposes). If a subject has replicated measurements at a postbaseline time point, then the median of the values will be used in data analyses. The sweat chloride results for the left and right arms will be averaged and used in the analysis if the sweat chloride values for the left and right arms are both $\geq 15~\mu L$; if only 1 arm is $\geq 15~\mu L$, then only that value will be used. Note: Any sweat chloride concentration values reported as <10~mmol/L or >160~mmol/L will be considered missing.

Descriptive summary statistics (n, mean, SD, SE, median, minimum, and maximum), along with the 95% confidence interval and within-group *P* value based on Normal approximation, will be provided for absolute change from baseline in sweat chloride at Week 24.

In addition, descriptive summary statistics, along with 95% confidence interval based on Normal approximation, will be provided for all other visits.

Additional analysis of the primary endpoint will be described in the SAP.

12.3.3.2.2 Absolute Change From Baseline in BMI/BMI-for-Age Z-score at Week 24

Descriptive summary statistics (n, mean, SD, SE, median, minimum, and maximum), along with the 95% confidence interval and within-group *P* value based on Normal approximation, will be provided for absolute change from baseline in BMI and BMI-for-age z-score at Week 24.

In addition, descriptive summary statistics, along with 95% confidence interval based on Normal approximation, will be provided at all other visits.

12.3.3.2.3 Absolute Change From Baseline in Weight/Weight-for-Age Z-Score at Week 24

Descriptive summary statistics (n, mean, SD, SE, median, minimum, and maximum), along with 95% confidence interval and within-group *P* values based on Normal approximation, will be provided for absolute change from baseline in weight and weight-for-age z-score at Week 24.

In addition, descriptive summary statistics, along with 95% confidence interval based on Normal approximation, will be provided at all other visits.

12.3.3.2.4 Absolute Change From Baseline in Stature/Stature-for-Age Z-score at Week 24

Descriptive summary statistics (n, mean, SD, SE, median, minimum, and maximum), along with 95% confidence interval and within-group *P* values based on Normal approximation, will be provided for absolute change from baseline in stature and stature-for-age z-score at Week 24.

In addition, descriptive summary statistics, along with 95% confidence interval based on Normal approximation, will be provided at all other visits.

12.3.3.2.5 Analysis of Pulmonary Exacerbation-related Other Secondary Pharmacodynamic Variables

- Time-to-first pulmonary exacerbation through Week 24: Time-to-first pulmonary exacerbation will be analyzed using Kaplan-Meier method. Cumulative incidence of pulmonary exacerbation will be summarized and plotted. Subjects without an exacerbation by Week 24 Visit will be censored at Week 24 Visit or at the last visit before the Safety Follow-up Visit for subjects with missing Week 24 Visit.
- Number of pulmonary exacerbations through Week 24: The number of pulmonary exacerbations through Week 24 [inclusive] (including both on-treatment events and events after treatment discontinuation), normalized by the time spent in the study (Week 24 date first dose date +1), will be summarized.
- Number of CF-related hospitalizations through Week 24: For the number of CF-related hospitalizations through Week 24 [inclusive], the analysis will be similar to the analysis of the number of pulmonary exacerbations through Week 24.

12.3.3.2.6 Absolute Change in FE-1 Levels From Baseline at Week 24

Descriptive summary statistics (n, mean, SD, SE, median, minimum, and maximum), along with 95% confidence interval and within-group *P* values based on Normal approximation, will be provided for absolute change from baseline in FE-1 levels at Week 24. In addition, descriptive summary statistics, along with 95% confidence interval based on Normal approximation, will be provided at all other visits.

Number and percentage of subjects with pancreatic insufficiency, defined as having FE-1 level $<200 \mu g/g$, will be provided at Week 24 and at baseline. The within-group shift will be tested based on McNemar's test.

12.3.3.2.7 Absolute Change in Serum Levels of IRT From Baseline Through Week 24

For each subject, the serum levels of IRT through Week 24 for each subject will be derived as the simple arithmetic mean at each visit (Day 15, Weeks 4, 8, 16, and 24), regardless of on-treatment measurement or measurement after treatment discontinuation. As long as there is at least 1 measurement available, the average will be calculated based on all available measurements. If all measurements are missing, then the average through Week 24 will be missing and the subject will not be included in the summary for the average through Week 24. The absolute change in serum levels of IRT from baseline through Week 24 will be

derived similarly as the simple arithmetic mean of the absolute change in serum levels of IRT from baseline at each visit.

Summary statistics, along with 95% confidence interval and within-group *P* values based on Normal approximation, for absolute change from baseline in serum levels of IRT through Week 24 will be provided.

In additional, summary statistics, along with 95% confidence interval based on Normal approximation, will be provided at each visit.

12.3.3.2.8 Change in Microbiology Culture From Baseline at Week 24

Raw values and change in microbiology from baseline at Week 24 will be summarized descriptively. The summary will be separated for each possibly-detected organism.

12.3.3.2.9 Absolute Change From Baseline in ppFEV₁ at Week 24

Summary statistics, along with 95% confidence interval and within-group *P* values based on Normal approximation, for absolute change from baseline in ppFEV₁ will be provided at Week 24.

In addition, summary statistics, along with 95% confidence interval based on Normal approximation, will be provided at all other visits.

12.3.3.2.10 Absolute Change in Sweat Chloride From Week 24 at Week 26

Summary statistics, along with 95% CI and within-group *P* values based on Normal approximation, for absolute change from Week 24 will be provided at Week 26.

12.3.3.2.11 Acceptability/Palatability of LUM/IVA Granules at Day 1

Summary statistics will be provided for the acceptability/palatability data.

12.3.3.2.12 Absolute Change From Baseline in LCI_{2.5} at Week 24

The LCI assessment at scheduled visits will be performed in multiple replicates. The LCI values at each visit included in the analysis will be the value calculated from the technically acceptable washout replicates.

When there is only one LCI value considered acceptable by the LCI central reader, the value will NOT be used. The assessment for that subject at the corresponding visit will be considered missing; when there are at least 2 LCI values considered acceptable by the LCI central reader, the arithmetic mean of the values from the accepted trials will be calculated as the value at the corresponding visit.

Descriptive summary statistics (n, mean, SD, SE, median, minimum, and maximum), along with 95% confidence interval and within-group *P* values based on Normal approximation, will be provided for absolute change from baseline in LCI_{2.5} at Week 24.

In addition, descriptive summary statistics, along with 95% confidence interval based on Normal approximation, will be provided at all other visits.

12.3.3.2.13 Absolute Change From Baseline in LCI_{5.0} at Week 24

Analysis of absolute change in LCI_{5.0} from baseline at Week 24 will be similar to the analysis of absolute change in LCI_{2.5} from baseline at Week 24.

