8.1.2 Part B

Approximately 56 subjects are planned for enrollment. Assuming a 10% dropout rate, approximately 50 subjects should complete Part B; at least 10 subjects must be <3 years of age at screening. Subjects should be ≥3 years of age at screening for enrollment in the optional LCI Substudy at a subset of sites. Additional subjects may be enrolled at the sponsor's discretion to achieve up to 30 subjects in the LCI Substudy.

Part B includes the following:

[figure not shown]
- Screening Period (Day -28 through Day -1)
- Treatment Period (Day 1 through Week 24 ± 5 days)
- Washout Period (Week 24 to Week 26 ± 4 days)
- Safety Follow-up Visit (Week 26 [2 weeks ± 4 days after the last study dose of LUM/IVA])

Figure 8-2 depicts the schematic for the Part B study design. Procedural details are described in the following sections:

- Section 10.2.2 for dose administration;
- Section 8.1.3 for the Screening Period;
- Section 8.1.7.2 for the Treatment Period;
- Section 8.1.8.2 for the Washout Period;
- Section 8.1.9.2 for the Safety Follow-up; and
- Section 8.1.10.2 for Early Termination of Treatment (ETT).

Subjects who have completed the required visits in Part B may be eligible to enroll in the Treatment Cohort or Observational Cohort of an Extension Study to evaluate long-term treatment with LUM/IVA; enrollment will be based on the eligibility criteria. The Treatment Cohort will enroll subjects who completed LUM/IVA treatment and the Safety Follow-up Visit in Part B. The Observational Cohort will enroll subjects who received at least 4 weeks of LUM/IVA treatment in Part B and completed visits up to the Safety Follow-up Visit, if applicable, in Part B, but do not meet eligibility criteria for enrollment into the Treatment Cohort. The Safety Follow-up Visit, if applicable, is the last visit for Part B, and should also be the Day 1 Visit in the Extension Study.

Figure 8-2 Schematic of Study Design for Part B

ETT: Early Termination of Treatment; IVA: ivacaftor; LCI: lung clearance index; LUM: lumacaftor; q12h: every 12 hours Notes: Approximately 56 subjects are planned for enrollment. Assuming a 10% dropout rate, approximately 50 subjects should complete Part B; at least 10 subjects must be <3 years of age. Subjects should be ≥3 years of age for enrollment in the optional LCI Substudy at a subset of sites. Additional subjects may be enrolled at the sponsor's discretion to achieve up to 30 subjects in the LCI Substudy.

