11.6.7 Spirometry

Part A and Part B

Spirometry will be performed according to the American Thoracic Society Guidelines⁴¹ at the time points noted in Table 3-1, Table 3-2, Table 3-3, and Table 3-4, according to the additional guidelines that follow. In Part A and Part B, spirometry will only be performed on subjects who are ≥ 3 years of age at screening of the corresponding part.

Pre-bronchodilator spirometry is defined as spirometry testing performed for subjects who have

- withheld their short-acting bronchodilator (e.g., albuterol) or anticholinergic (e.g., Atrovent®) for more than 4 hours before the spirometry assessment;
- withheld their long-acting bronchodilator (e.g., salmeterol) more than 12 hours before the spirometry assessment; and
- withheld their once-daily, long-acting bronchodilator (e.g., tiotropium bromide [Spiriva®]) for more than 24 hours before the spirometry assessment.

During the Screening Period, spirometry assessments may be performed pre- or post-bronchodilator. At all other visits, all spirometry assessments should be performed "pre-bronchodilator." During the Treatment Period, spirometry assessments must be

performed before dosing, unless noted otherwise. In the event that a subject forgets to withhold bronchodilator(s), spirometry should be performed according to the following:

- If a subject's Day 1 spirometry is pre-bronchodilator, but on a subsequent visit, the subject forgets to withhold bronchodilator use, a post-bronchodilator spirometry will be obtained for that visit only, and the visit will not be rescheduled.
- If on Day 1, the subject forgets to withhold his/her dose of bronchodilator, spirometry should be performed post-bronchodilator and all subsequent spirometric measurements (according to the Schedule of Assessments detailed in Table 3-2 and Table 3-4) should be performed post-bronchodilator.
- Each spirometry assessment will be recorded in the source documents as pre-bronchodilator or post-bronchodilator.

The parameters listed below will be normalized using the standards of GLI.⁴²

- FEV₁ (L)
- Forced vital capacity (FVC) (L)
- FEV₁/FVC (ratio)
- Forced expiratory flow (FEF_{25%-75%}) (L/s)

The central spirometry service will provide all sites with spirometers and associated materials to be used for all study assessments. Spirometry data will be transmitted to a centralized spirometry service for quality review.

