12.2 Analysis Sets

Part A

All Subjects Set is defined as all subjects who have signed informed consent (and assent, if applicable) and enrolled or dosed in Part A.

Safety Set will include all subjects who received at least 1 dose of study drug in Part A. The safety analyses will be based on the Safety Set overall, unless otherwise specified. In addition, the summary by the dosing groups (LUM 100 mg/IVA 125 mg q12h and LUM 150 mg/IVA 188 mg q12h) at enrollment determined by weight at the Screening Visit will be provided as supplementary information.

Part B

All Subjects Set is defined as all subjects who have signed informed consent (and assent, if applicable) and enrolled or dosed in Part B.

Safety Set will include all subjects who received at least 1 dose of study drug in Part B. The safety analyses will be based on the Safety Set overall, unless otherwise specified. If the weight-based 2 doses are used in Part B, the summary by the dosing groups (LUM 100 mg/IVA 125 mg q12h and LUM 150 mg/IVA 188 mg q12h) at enrollment determined by weight at Screening Visit will be provided as supplementary information.

Full Analysis Set (FAS) will include all enrolled subjects in Part B who are exposed to any amount of study drug in Part B. PD analyses (except LCI) will be based on the FAS.

LCI Substudy Set will include all subjects who have signed informed consent (and assent, if applicable) to the optional LCI Substudy in Part B and enrolled and dosed in Part B. LCI-related analysis will be based on the LCI Substudy Set.

Subject data listings for both Part A and Part B will be the referenced using the All Subjects Set in the corresponding part, unless otherwise specified.

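### Confidence intervals and P values for LCI and ppFEV1 rest on a Normal approximation; read literally (z = 1.96), the 95% intervals cover about 94% at the planned sizes

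*Protocol*

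**What the plan says.** Three sections of the protocol fix the method for lung-function change from baseline at Week 24.

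- Section 12.3.3.2.12 (LCI2.5): a 95% confidence interval and within-group P "values based on Normal approximation, will be provided for absolute change from baseline in LCI_{2.5} at Week 24".
- Section 12.3.3.2.9 (ppFEV1): a 95% confidence interval and within-group P "values based on Normal approximation, for absolute change from baseline in ppFEV₁ will be provided at Week 24".
- Section 12.3.3.2.13 (LCI5.0): "Analysis of absolute change in LCI_{5.0} from baseline at Week 24 will be similar to the analysis of absolute change in LCI_{2.5" (the sentence continues with the same baseline and visit).

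None of the three names the t distribution, and none writes z or 1.96.

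The sample sizes come from elsewhere. Section 8.1.2 states: "Approximately 56 subjects are planned for enrollment". It also states that "at least 10 subjects must be <3 years of age at screening", and, for the optional substudy, "Additional subjects may be enrolled at the sponsor's discretion to achieve up to 30 subjects in the LCI Substudy". Section 11.6.7 says that "spirometry will only be performed on subjects who are" aged 3 or older at screening. Section 12.2 says that "PD analyses (except LCI) will be based on the FAS", so ppFEV1 is nominally a full analysis set endpoint even though the youngest children have no measurement. Section 8.3.3 expects only a minority of the study population to produce reproducible spirometry.

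**The concern.** When the standard deviation is estimated from the same small sample, the standardised mean change follows a t distribution with n - 1 degrees of freedom, not a standard Normal. A multiplier of 1.96 ignores the uncertainty in the standard deviation, so the interval is too narrow and the P value too small. The gap grows as n falls, which is why the point is raised for LCI and ppFEV1.

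At stake is whether an interval labelled 95% has that level, and whether a borderline within-group P value falls on the right side of 0.05. The phrase also leaves two analyses open that give slightly different answers from the same data.

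**Working it through.** **The plan's own figures.** The protocol gives no coverage figure beyond the nominal 95%. Its only sample-size probabilities (Section 12.1) reproduce: 1 - 0.95^50 = 92.3% and 1 - 0.90^50 = 99.5%. They concern adverse events and do not bear on this point. The enrolment figure also agrees: 50 / 0.9 = 55.6, rounded up to 56.

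**Sample sizes used.**

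- LCI, planned maximum: 30 (Section 8.1.2).
- LCI after dropout: 30 × 0.9 = 27. This assumes the protocol's 10% rate applies to the substudy.
- ppFEV1, aged 3 or older: 56 - 10 = 46, taking the minimum number under 3.
- ppFEV1 after dropout: 46 × 0.9 = 41.4, about 41.
- ppFEV1 if the expected minority holds: fewer than half of 56, so at most 27. Section 8.3.3 states this as an expectation, not as a cap or an analysis rule.
- Endpoints measured in all subjects, for comparison: 50 to 56.
- n = 20 and n = 10 are assumptions that show the trend. The protocol states no evaluable number. Section 12.3.3.2.12 also discards an LCI visit with only one acceptable value, which can lower n further.

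**Formulas.** For normally distributed changes with an estimated standard deviation, the coverage of mean ± 1.96 × SE is

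P(|t with n - 1 df| < 1.96) = 2 × F(1.96; n - 1) - 1,

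where F is the t distribution function. This does not depend on the true standard deviation. The width ratio is the 97.5% t quantile divided by 1.96.

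| n | Coverage with z | t quantile | t width / z width |
|---|---|---|---|
| 56 | 94.5% | 2.004 | 1.022 |
| 50 | 94.4% | 2.010 | 1.025 |
| 46 (ppFEV1) | 94.4% | 2.014 | 1.028 |
| 41 (ppFEV1, dropout) | 94.3% | 2.021 | 1.031 |
| 30 (LCI maximum) | 94.0% | 2.045 | 1.044 |
| 27 (LCI, dropout; ppFEV1, minority) | 93.9% | 2.056 | 1.049 |
| 20 (assumed) | 93.5% | 2.093 | 1.068 |
| 10 (assumed) | 91.8% | 2.262 | 1.154 |

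The two-sided error rate is the complement: 6.0% at n = 30 and 5.6% at n = 46, against a nominal 5%.

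**Simulation check.** With 400,000 Normal samples per size at n = 46, 41, 30 and 27, the z interval agreed with the formula to within 0.1 percentage point, and the t interval covered 95% to within 0.1 point.

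**Effect on a borderline P value.** A test statistic of 2.00 gives a two-sided P of 0.046 by z. By t it is 0.052 at n = 46 or 41, 0.055 at n = 30 and 0.056 at n = 27.

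**The case against.** The best reply is that nothing here is plainly wrong. The protocol never writes 1.96, and the phrase can be shorthand for a parametric analysis that assumes approximate normality, run as a one-sample t. Section 12.3 leaves analysis details to the statistical analysis plan, which could settle the matter without contradicting the protocol. Even on the literal reading, the loss is 1.0 point at n = 30 and 0.6 at n = 46, on secondary endpoints in an open-label, single-arm study with no success criterion tied to them. A test statistic of 2.00 is chosen to sit at the threshold.

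Singling out ppFEV1 can also be challenged. Coverage at 46 (94.38%) hardly differs from coverage at 50 (94.43%), and 46 is not a firm ceiling, because subjects added to fill the LCI Substudy must be aged 3 or older. The dropout-adjusted sizes are assumptions too, since subjects who stop treatment are asked to complete assessments through Week 24. Finally, if changes are skewed, a t interval does not guarantee 95% either.

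Most of this stands as a limit on size. It does not remove the point. The protocol does not leave the reference distribution open: it names one, and the name taken at its word gives the narrower interval. If the analysis plan uses t, the protocol wording should match it; if it follows the protocol literally, the shortfall is real. Skewness could move coverage either way, but under the normality that the calculation assumes, t is exact and z is not.

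**Conclusion.** The point holds as a minor one. On the literal reading, nominal 95% intervals for LCI2.5 and LCI5.0 cover 94.0% at the planned maximum of 30 and 93.9% at 27. For ppFEV1, coverage is 94.4% at 46, 94.3% at 41 and 93.9% if only 27 subjects contribute. These figures assume normally distributed changes and a multiplier of 1.96. If a one-sample t interval was intended, there is no loss of coverage and only the wording needs correcting. The same phrase governs the other continuous pharmacodynamic changes, where the shortfall at n = 50 to 56 is only about half a point. The primary safety objective is unaffected, and no stated decision rests on these P values.

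**What to change.** In Sections 12.3.3.2.9 and 12.3.3.2.12, and so by reference in 12.3.3.2.13, replace the reference to a Normal approximation with: *based on the one-sample t distribution with n - 1 degrees of freedom*, for both the confidence intervals and the within-group P values. For consistency, use the same wording for the other continuous pharmacodynamic change endpoints, where the multiplier differs by only about 2%. The statistical analysis plan should say the same.

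The cost is one wording change, with no new data, visits or subjects. On the literal reading, intervals become 4.4% wider at n = 30 and 2.8% wider at n = 46, and P values become slightly larger.
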